#### LIST OF ABBREVIATIONS

AE Adverse Event/Adverse Experience

CFR Code of Federal Regulations

CONSORT Consolidated Standards of Reporting Trials

COVID-19 coronavirus disease 2019

SRS-CoV SARS coronavirus (i.e. circa 2003) SARS-CoV-2 SARS coronavirus 2 (i.e. circa 2019)

CRF Case Report Form

CRO Contract Research Organization
DCC Data Coordinating Center

DSMB Data and Safety Monitoring Board eCRF Electronic Case Report Form
GCP Good Clinical Practice

GCP Good Clinical Practice ICF Informed Consent Form

ICH International Conference on Harmonization IEC Independent or Institutional Ethics Committee

IRB Institutional Review Board

MERS-CoV Middle East respiratory syndrome coronavirus

MUHC McGill University Health Center N Number (typically refers to subjects)

PHI Protected Health Information

PI Principal Investigator

RI-MUHC Research Institute of the McGill University Health Centre

SAE Serious Adverse Event

SOP Standard Operating Procedure WHO World Health Organization

[figure not shown]
# **Summary**

Full Title:	Mild - CONTAIN CiclesOnide cliNical TriAl covId-19 treatmeNt
Short Title:	Mild - CONTAIN
Clinical Phase:	II
Sponsor:	Research Institute of the McGill University Health Centre
Principal Investigator:	[name] [name], FRCPC
Co-Investigators	[name]; [name]; [name]; [name] Statistician; [name], PhD; [name], [name]; [name]; [name]; [name]
Study Population	>=18 years of age Laboratory confirmed COVID-19 as determined by PCR within 5 days of enrolment
	Early mild symptomatic patients: Non-hospitalized adults or health care workers with COVID-19 (n= 159 per arm)
Objective	Evaluate whether early treatment with inhaled and nasal ciclesonide improves symptoms at day 7 in early mild to moderate symptomatic patients
Study Design	Adaptive, Double-blind, randomized placebo-controlled clinical trial  Pragmatic trial with internet based self-referral, electronic consent, virtual online follow-up and self-reported outcomes.  Study medicine delivered by courier to consented participants.  Follow up through 7 days and 14 days and 30 days after randomization.

Intervention Arm:	Ciclesonide (600mcg BID inhaled with aerochamber) plus nasal ciclesonide (200 mcg DIE) for 14 days					
Control Arm:	Placebo (delivered by metered dose inhaler BID with aerochamber) plus intranasal saline DIE for 14 days.					
Primary Endpoint	Proportion of participants with no symptoms of cough, fever or dyspnea at day 7.					
Secondary Endpoints	
 
Hospitalization for SARS-CoV-2 related illness at day 14
 
Primary outcome (proportion of patients with no cough fever or dyspnea) measured at day 14
 
Mortality at day 14 and 29
 
Ordinal Scale for Evaluating subject Clinical Status
 
PROMIS dyspnea, anxiety and sleep at day 7 and 14.
 
Visual Analog scale from 0-10 indicating improvement in symptoms at day 7 and 14.
 
Time to symptom resolution (post-hoc)
 
					
Duration of Participation	
 
Recruitment and follow up will be internet-based.
 
Clinical Assessment: 14 days post ciclesonide initiation to assess final outcome
 
Clinical assessment at Day 29: Clinical assessment, Follow up vital status, self reported hospitalization
 
					
Inclusion Criteria	Symptomatic adult patients positive by PCR for COVID-19 within 5 days of enrollment with fever, cough or shortness of breath (day 6 if shipped same day). Provision of Informed Consent					
	At Day 0, patients should be at home					

Exclusion Criteria	
 
Already on inhaled corticosteroid medication
 
Currently using systemic steroids (oral or intravenous or intramuscular such as Prednisone) or use of steroids 7 days prior to enrolment
 
Severely ill patients at enrollment (i.e., admitted to ICU at admission)
 
Unable to self-administer the inhaler
 
Known or suspected pregnancy and breastfeeding
 
Known allergy to study medication or its components (non-medicinal ingredients; including lactose allergy (type I))
 
Patients with untreated fungal, bacterial or tubercular infections of the respiratory tract
 
Current hospitalization
 
Current use of oxygen at home or in hospital
 
Vaccinated for COVID-19
 

Stratification	Randomization will be stratified by sex
Statistical Assumptions	With 159 subjects per arm we will be able to detect an absolute increase of 15% in the number of patients with resolved symptoms at day 7.
Safety	Safety of the intervention will be assessed by the cumulative incidence of Grade 3 and 4 AE and SAEs using the Division of AIDS Table for Grading Severity of Adult and Pediatric Adverse Events version 2.1

# 2 BACKGROUND INFORMATION AND SCIENTIFIC RATIONALE

## **2.1** Background Information

#### Significance of Research Question/Purpose:

Coronaviruses are a large family of viruses that usually cause mild to moderate respiratory illness. However, three major coronaviruses capable of causing serious disease have been identified in the last two decades, namely SARS-CoV, MERS-CoV and most recently, the novel SARS-CoV-2. First identified in December 2019 in the province of Wuhan, China, SARS-CoV-2 has rapidly emerged as a highly transmissible and potentially fatal virus, causing COVID-19. It has shown to be capable of causing mild to severe disease, requiring oxygen therapy, hospitalization, intensive care, mechanical ventilation, and has led to widespread illness and death.

The number of global COVID-19 cases has rapidly progressed in the last few months. The outbreak was declared a Public Health Emergency of International Concern on January 30, 2020, and on March 11th, the World Health Organization declared COVID-19 a global pandemic.

As of April 20, 2020, there were 2.36 million confirmed COVID-19 cases worldwide, and 164 656 deaths related to COVID-19. In Canada, there were 34 777 cases and 1580 deaths(1). In an effort to prevent disease progression and overload of healthcare systems, provincially and internationally, authorities have held multiple public services and public spaces, postponed various in and out-hospital services and have imposed travel restrictions.

Only one antiviral therapy is currently approved in Canada for patients with mild to moderate symptoms of COVID-19 (Bamlanivimab) (2) however it is not widely available due to costs and the need for IV infusion. The standard of care remains supportive measures and quarantine of infected persons for a minimum of 14 days.

Global efforts to evaluate novel antivirals and therapeutic strategies to treat COVID-19 have intensified and there is an urgent public health need for rapid development of novel interventions.

#### Preliminary Data:

[figure not shown]
Like MERS-CoV and SARS-CoV (3), SARS-CoV-2 virus is a betacoronavirus. It has 79.5% sequence identity with that of human SARS-CoV (4).

Ciclesonide has shown *in vitro* activity against MERS-CoV, SARS-CoV and SARS-CoV-2. In vitro, the viral replication of SARS-COV-2 showed 2-fold reduction at 27 hours post infection. (5) In Vero cells, the half maximal inhibitory concentration (IC50) of ciclesonide against SARS-CoV-2 was 4.33 mcM (5). The NSP15 homo-hexamer was possibly the target of ciclesonide. Other steroids tested (cortisone, prednisolone, fluticasone, dexamethasone) showed no significant effect on viral replication suggesting the ciclesonide effect is drug specific and not a steroid class effect (6). Subsequently, reduced viral load of SARS-CoV-2 has been shown to be associated with reduced clinical disease severity (7).

## **Existing Literature:**

In February 2020, 5406 compounds (including 2069 FDA approved drugs) were tested for anti-MERS-CoV activity by determining viral spike protein expression in infected Vero cells and 12 compounds were selected for having demonstrated a greater than 70% anti MERS-CoV activity. Ciclesonide was identified as one of the drugs that inhibit MERS-CoV replication, similar to chloroquine (8).

The in vitro effect of different steroids on MERS-COV, SARS-CoV and SARS-CoV-2 showed that ciclesonide was suppressing the viral replication of those 3 coronaviruses with low cytotoxicity. For SARS-CoV-2, the viral replication was reduced 2-fold at 27 hours post infection (Figure 1). The NSP15 homo-hexamer was possibly the target of ciclesonide. Other steroids tested against MERS-CoV (cortisone, prednisolone, fluticasone, dexamethasone, mometasone) showed no significant effect on viral replication (except for mometasone) suggesting the ciclesonide effect is drug specific and not a steroid class effect, so these steroids were not tested against SARS-CoV-2 (Figure 2) (6).

**Figure 1. - Antiviral effects of steroids on SARS-CoV-2.** (a) Intracellular SARS-CoV-2 RNA (6 hpi). VeroE6/TMPRSS2 cells were infected with SARS-CoV-2 at MOI = 1 in the presence of  $10\mu\text{M}$  compounds for 6 h. Cellular viral RNA was quantified by real-time PCR using the E gene primer/probe set. (b) Culture Medium SARS-CoV-2 RNA (27 hpi). VeroE6/TMPRSS2 cells were infected with SARS-CoV-2 at MOI = 0.01 in the presence of ciclesonide for 27 h. Viral RNA in culture medium was quantified by real-time PCR using the E gene primer/probe set. Cell viability in the presence of ciclesonide was quantified at 27 hpi by WST assay (1).

[figure not shown]

Figure 2- Antiviral effects of steroids on SARS-CoV-2. (a) Intracellular SARS-CoV-2 RNA (6 hpi). VeroE6/TMPRSS2 cells were infected with SARS-CoV-2 at MOI = 1 in the presence of  $10\mu M$  compounds for 6 h. Cellular viral RNA was quantified by real-time PCR using the E gene primer/probe set.

In order to determine drug antiviral activity specific to SARS-CoV-2, 3000 FDA and IND-approved drugs were screened and ciclesonide showed a potent antiviral effect (IC50=4.33 mcM; Figure 3) in addition to its intrinsic anti-inflammatory function (5).

[figure not shown]

Figure 3 - (part of Figure 1B from reference 5) Dose response curve analysis by immunofluorescence for 45 drugs that were tested in this study. The blue squares represent inhibition of virus infection (%) and the red triangles represent cell viability (%). Means  $\pm$  SD were calculated from duplicate experiments

Subsequently, reduced viral load of SARS-CoV-2 has been shown to be associated with reduced clinical disease severity (7).

#### 2.2 Rationale

Current standard of care is supportive care after the diagnosis of COVID-19.

Ciclesonide is a corticosteroid currently used for asthma (in its inhaled form) and nasal rhinitis (in its spray form). It has a very good safety profile. Much higher doses of ciclesonide (up to a single inhalation of 3200 mcg) have been administered to healthy volunteers and were well tolerated (9). As such, inhaled and nasal ciclesonide at the doses of 600mcg BID for 2 weeks will have few adverse events. The usual doses for ciclesonide are:

Standard asthma treatment (ciclesonide, *Alvesco*):

- The recommended dose range for ciclesonide in inhalation is 100 to 800 mcg daily (9).
- The recommended starting dose for most asthmatic patients is 200 mcg daily in Canada (10).
- The maximum dose of 800 mcg daily should be administered as 400 mcg twice daily (9).

Standard allergic rhinitis treatment (ciclesonide, *Omnaris*) (11):

- The recommended dose of OMNARIS is 200 mcg per day administered as 2 sprays (50 mcg/spray) in each nostril once daily.
- The maximum total daily dosage should not exceed 2 sprays in each nostril (200 mcg/day)

As the specific dose of ciclesonide to decrease SARS-CoV-2 is unknown, we planned to give a higher dose than the maximum approved dose for asthma of inhaled ciclesonide (1200 mcg daily administered as 600 mcg twice daily) plus the usual dose of intranasal ciclesonide (200 mcg/day) for 14 days. Given viral replication begins in the nasal cavity and then progress to the lungs, we have chosen to administer ciclesonide both intranasally and inhaled. This dose has been chosen in order to maximize deposition of the study drug in the lower airways. Although the usual dose of ciclesonide for asthma is 400 mcg twice daily (for a total of 800 mcg/day), single doses (up to 3200 mcg) have been administered to healthy subjects without significant side effects (9).

The in vitro replication of SARS-CoV-2 was reduced by twice in 27h, so we expect the effect of ciclesonide to be rapid. Moreover, as we hypothesize its antiviral effects will affect the nasal/upper airways replication of the virus, it should be more effective at the beginning of the disease compared to when the virus has spread to the lung. Therefore, we aim to recruit patients at the beginning of their disease (within 5 days of positive SARS-CoV-2 PCR) and to have a rapid benefit on symptom severity (at 7 days of enrollment). However, multiple complications of COVID-19 appear after the first 7 days (Zhou and al., 2020) so we will continue our treatment for a total of 14 days (4).

The proposed treatment will allow faster symptom resolution of COVID-19 symptoms in mildly symptomatic outpatients and return to work for healthcare workers and essential workers.

In Canada we will be using DIN 02285614 / Alvesco) and intranasal Ciclesonide (DIN 02303671/ Omnaris) as the active drug and a placebo inhaler (NDC 70515-710-01) as the placebo.

#### 2.3 Potential Risks and Benefits

#### 2.3.1 Potential Risks

Ciclesonide is a drug currently used for asthma maintenance treatment (in its inhaled form) and nasal rhinitis. It has been approved by Health Canada in 2008 in this setting. It has a very good safety profile with mainly local possible side effects. The principal sides effects as listed on the monograph are:

#### **Common Clinical Trial Adverse Drug Reactions (≥1% - <10%)**

Respiratory: Paradoxical bronchospasm (1.6%), Dysphonia (1.0%).

#### **Uncommon Clinical Trial Adverse Drug Reactions (≥0.1% to <1%)**

Cardiovascular: Palpitations (0.1%).

Eye: Cataract subcapsular (0.1%).

Gastrointestinal: Nausea (0.2%), Dry mouth (0.1%), Dyspepsia (0.1%)

Infections: Oral candidiasis (0.6%), Candidiasis (0.1%), Oral fungal infection (0.1%),

Pharyngitis (0.1%).

Injury: Contusion (0.1%).

Investigations: ALT increased (0.1%), Gamma-glutamyltransferase increased (0.1%)

Weight increased (0.1%)

Nervous System: Headache (0.4%), Dysgeusia (0.3%), Dizziness (0.1%).

Respiratory, thoracic and mediastinal disorders: Pharyngolaryngeal pain (0.4 %), Throat irritation (0.3%), Dry throat (0.1%).

Skin: Rash (0.1%).

The incidence of local oropharyngeal adverse reactions in ALVESCO-treated patients was low and comparable to placebo.

The risk of thrush (appearance of Candida albicans in the mouth and throat) is rare but can be further reduced by the use of an aerochamber and a proper mouth rinsing after using Ciclesonide.

The contraindications to Ciclesonide, as listed on the monograph:

CONTRAINDICATIONS ALVESCO (ciclesonide) is contraindicated in patients with known hypersensitivity to any of the ingredients.

ALVESCO is not to be used in the primary treatment of status asthmaticus or other acute episodes of asthma, or in patients with moderate to severe bronchiectasis.

OMNARIS (ciclesonide) is contraindicated in patients with hypersensitivity to any of the ingredients.

OMNARIS should be used with caution, if at all, in patients with active or quiescent tuberculosis infections of the respiratory tract.

#### 2.3.2 Known Potential Benefits

- There are no proven benefits in humans for treatment of COVID-19
- At the Kanagawa Prefectural Ashigarakami Hospital, in Japan, three patients with COVID-19 were treated with inhaled Alvesco and clinically improved (12).
- In vitro antiviral activity against SARS-CoV and SARS-CoV-2 viruses
- Ciclesonide both in inhalation and spray have a long history of safe, effective use is asthma and allergic rhinitis, both acutely and long-term.
- 2 randomized clinical trials on Ciclesonide for COVID-19 are about to start, one in mild patients taking place in Korea (13) and one pre-symptomatic patients, taking place in Japan (14).
- Recent studies have shown potential direct-acting antiviral activity in addition to its intrinsic anti-inflammatory function (5).

# **3** OBJECTIVES

#### 3.1 Study Objectives

To evaluate whether early treatment with inhaled and nasal ciclesonide results in symptom resolution at day 7 in early mild symptomatic patients (particularly dyspnea)

#### **3.2** Study Outcome Measures

#### **3.2.1** Primary Outcome Measures

**Primary outcome** is defined as the proportion of patients with resolved respiratory symptoms (fever, cough, shortness of breath, chest congestion or chest tightness) at day 7.

[figure not shown]
#### **3.2.2** Secondary Outcome Measures

- a) Hospitalization for SARS-CoV-2 related illness at day 14
- b) Primary outcome (proportion of patients with no cough, fever or dyspnea) measured at day 14
- c) Mortality at day 14 and 29
- d) Ordinal Scale for Evaluating subject Clinical Status (overall feeling) (see Appendix 2) measured on day 0, 1, 3, 5, 7, 14 and 29: We will evaluate the proportion who are reporting that they are "very much improved" or "much improved" by day 7 and day 14 (vs. not).
- e) PROMIS dyspnea, anxiety and sleep (respectively). We will look at the questionnaires at day 7 and at day 14 and compare the proportions between groups with a 3 point or higher change (compared to day 0 and using the t-score adjusted for population). We will also report the mean T scores. Raw scores are converted to standardized T scores using

- calibrated algorithms for the general population. They are standardized scores with a mean of 50 and SD of 10; 45 to 55 on a PROMIS T score is considered the normal range. 55-60 is mild levels of symptoms (anxiety, sleep, dyspnea), 60-70 is moderate, and 70+ is severe. A meaningful change will be considered a 3 point change on the T score.
- f) Visual Analog scale from 0-10 indicating improvement in symptoms measured at day 0, 1, 3, 5, 7, 10, 14 and 29; analysis will look at resolution of symptoms at day 7 and day 14, and resolution of cough at day 7 and 14.
- g) Time to symptom resolution (post-hoc)

Assessment of outcome measures will be primarily by self-report. As necessary, COVID-19 disease will be verified from public health records, medical records, or death certificates. The primary analysis will use PCR+ confirmed disease.

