# 7 STUDY SCHEDULE

- Information includes consent document. The patient signs electronically in the application after answering questions which confirm comprehension.
- If eligible, drug is prescribed, they are randomized, and shipping is arranged for study drug or placebo

Questionnaire	Day 0	Day1	Day 3	Day 5	Day 7	Day 10	Day 14	Day 29
Eligibility (screening form)	X							
Enrolment form (for eligible patients)	X							
Follow up questionnaire (MESA COVID 19)	X	X	X	X	X	X	X	X
Severity of overall symptoms	X	X	X	X	X	X	X	X
Dyspnea characteristics	X	X	X	X	X	X	X	X
Dyspnea severity	X	X	X	X	X	X	X	X
Visual analog scale for individual symptoms	X	X	Х	X	X	X	Х	X
Sleep PROMIS scale	X	X	X	X	X	X	X	X
Anxiety PROMIS scale	X	X	X	X	X	X	X	X

WHO ordinal scale	X	X	X	X	X	X	X	X
Hospitalization/Oxygen		X	X	X	X	X	X	X
use query								
Side effects query		X	X	X	X	X	X	X
Mortality							X	X
Subject orientation of							X	
the type of the study								
drug (placebo or active								
drug)								

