#### **Secondary Analyses:**

Proportions meeting each secondary outcome will be analyzed by binomial regression adjusting for stratification and the differences will be reported as an absolute risk difference and 95% CI.

The post-hoc analysis of time to symptom resolution will use the Kaplan Meier plot.

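### PROMIS T scores are compared between arms only as an undirected 3-point change; no between-arm mean difference adjusted for the Day 0 score is planned

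*Combined protocol and SAP*

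**What the plan says.** Section 3.2.2, item e, sets out one between-arm comparison for the three PROMIS domains (dyspnea, anxiety, sleep) at Days 7 and 14. The plan is to "compare the proportions between groups with a 3 point or higher change", and the change is "compared to day 0 and using the t-score adjusted for population". The means appear once: "We will also report the mean T scores". The score runs upward with severity: "55-60 is mild levels of symptoms (anxiety, sleep, dyspnea), 60-70 is moderate, and 70+ is severe". Neither the comparison rule nor the sentence defining a meaningful change gives a sign.

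The Secondary Analyses paragraph of section 11.4 reads "Proportions meeting each secondary outcome will be analyzed by binomial regression adjusting for stratification", with the result given as an absolute risk difference and 95% CI. Apart from a Kaplan-Meier plot for the post-hoc time-to-resolution outcome, no other method is given for a secondary outcome, so there is no model for a continuous score.

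The schedule in section 7 lists "Sleep PROMIS scale" and "Anxiety PROMIS scale" at Day 0 and at every later contact. Its dyspnea rows, such as "Dyspnea severity", are not labelled PROMIS. That Day 0 PROMIS dyspnea was collected has to be inferred from item e.

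**The concern.** The Day 0 score enters the analysis only as the reference for a change, and that change is then cut at 3 points. The cut ignores how far a patient moved on either side of the threshold. The stratification factors do not include the baseline score, so the between-patient variation that Day 0 could explain stays in the error. Mean T scores by arm, without a difference and an interval, do not fill the gap. A real PROMIS benefit could be estimated too loosely to be recognised, although most or all of the data needed for a sharper estimate are already scheduled.

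Dyspnea is not a peripheral domain here: the objective in section 3.1 singles it out and the hypothesis in section 11.1 is about it.

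The missing direction is a smaller matter. The Summary, sections 3.1 and 11.1, and the neighbouring item d all point to improvement. Read literally, however, item e also counts patients who worsen by 3 points or more, and this leaves a choice open at analysis.

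**Working it through.** **The plan's own figure.** Section 11.2 gives no PROMIS calculation, but its primary sample size fixes the number of evaluable patients used below. For 65% vs 80%, two-sided 5% and 80% power, with pooled variance under the null:

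n = [1.96·√(2·0.725·0.275) + 0.842·√(0.65·0.35 + 0.80·0.20)]² / 0.15² = 138 per arm, 276 in total. Then 138 × 1.15 = 159 per arm, 318 in total. Both match the table.

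**Inputs for the illustration.** 138 evaluable per arm (276/2, section 11.2). SD 10 at each visit (item e gives this as the general-population value; its use for this trial is an assumption). All the rest is assumed: Day 0 to follow-up correlation r = 0.5, mean change −3 on placebo and −6 on active, normal scores, two-sided 5%, unpooled variance.

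**Formulas and base case.**

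- ANCOVA: SD·√(1−r²) = 8.66; SE = 8.66·√(2/138) = 1.043; z = 3/1.043 = 2.877; power 82%.
- Unadjusted mean change: SDc = SD·√(2(1−r)) = 10; SE = 1.204; z = 2.492; power 70%.
- Decrease of at least 3: P = Φ((−3−μ)/SDc), giving Φ(0) = 50.0% and Φ(0.3) = 61.8%; difference 11.8 points; SE = √[(0.25 + 0.236)/138] = 5.9 points; z = 1.987; power 51%.
- Change of at least 3 in either direction: worsening adds 1−Φ(0.6) = 27.4% on placebo and 1−Φ(0.9) = 18.4% on active; the rates become 77.4% and 80.2%; z = 0.564; power 9%.

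Patients per arm for the responder comparison to equal ANCOVA with 138: 138/(1.987/2.877)² = 138/0.477 = 289.

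In terms of estimation, the 95% CI half-width for the mean difference is 1.96 × 1.043 = 2.0 T points with ANCOVA and 1.96 × 1.204 = 2.4 without adjustment. For the responder difference of 11.8 percentage points it is 1.96 × 5.9 = 11.6.

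**Range.** Benefit 3 points; SD 7, 8.5 or 10; r 0.3, 0.5 or 0.7; placebo change −1, −3, −5 or −8 (36 scenarios); 138 per arm:

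| Analysis | Median power | Range |
|---|---|---|
| ANCOVA on Day 0 score | 94% | 74–100% |
| Unadjusted mean change | 85% | 56–100% |
| Decrease of at least 3 | 65% | 36–96% |

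The gap between ANCOVA and the responder comparison has a median of 30 percentage points (range 4 to 42). With benefits of 2, 3 and 4 points (108 scenarios) ANCOVA is ahead in all 108, by 0.1 to 42 points.

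**Bounded scores.** The base case was also simulated with an assumed baseline mean of 55 and an assumed floor. Power for ANCOVA, mean change and responder is about 79/66/46% with the floor at 35, and 81/65/42% with the floor at 40. The gap does not depend on unbounded scores.

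**Direction in a favourable case.** With SD 7, r = 0.7 and changes of −8 and −11, only 2.1% of placebo patients worsen by 3 or more. Power is 79% for a decrease, 69% for either direction and 99.9% for ANCOVA. The cost of the literal reading therefore depends heavily on how much patients improve on placebo.

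**The case against.** The strongest reply is that this is a choice of estimand. The plan states a threshold, a reference day, two time points, a model and an effect measure. A responder proportion is easy to read and fits a plan whose primary outcome and most other secondary outcomes are binary. That stands as a reason to keep the responder analysis. It does not explain why the means get no contrast.

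Section 11.4 plans estimates with intervals for secondary outcomes and names no test, so power is an indirect yardstick. This is fair, and wider uncertainty is the better description. The interval widths lead to the same conclusion.

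Every PROMIS input is assumed, and a uniform normal shift suits a mean contrast. In 8 of the 36 scenarios the responder comparison already has at least 80% power. Section 9.5 says enrolment dropped off, so 138 per arm may not have been reached. With an assumed 80 or 50 evaluable per arm, the base case gives ANCOVA 59% or 41% and the responder comparison 33% or 22%. The levels fall but the order does not change.

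Reporting means might have been meant to include a between-arm difference. The text does not exclude it, but names no model, interval or covariate.

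Finally, section 9.5 describes enrolment in the past tense, so an addition now cannot count as prospective. That is correct and limits the added analysis to a supportive role.

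**Conclusion.** The concern holds. The only specified between-arm PROMIS comparison is a dichotomised one, the Day 0 score is never a covariate, and the responder rule has no direction. The loss of precision is material: 82% vs 51% power in the base case, a median gap of 30 percentage points over the 36 scenarios with a 3-point benefit, and the same ordering in all 108 scenarios of the wider grid. These sizes rest on an assumed SD, correlation, placebo change and benefit, none of which the documents give for this trial. The precision advantage itself does not depend on having 138 per arm.

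The missing direction is a wording gap and would be minor alone. The 9% figure applies only to a reading that is almost certainly not intended. One secondary item is affected; the primary analysis and sample size are not. The change should be made because it is cheap, but it is not critical to the trial.

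**What to change.** In section 3.2.2, item e, define response as a decrease of at least 3 T-score points from Day 0, at Days 7 and 14, for each of dyspnea, anxiety and sleep. Give the proportion with an increase of at least 3 points descriptively, without a test.

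In section 11.4, add for each domain and day the adjusted difference in mean T score with 95% CI, from an ANCOVA on the Day 0 T score and the stratification factors actually used. The Summary gives sex only and section 7.2.1 gives study site and sex, so these must be reconciled first. Keep the responder analysis and present the ANCOVA beside it as supportive, with the date it was added. Confirm that Day 0 PROMIS dyspnea was collected; if it was not, limit the ANCOVA to sleep and anxiety.

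The cost is a few sentences and one standard model per domain and day, with no new data. The downside is six more contrasts (three domains by two days) and six descriptive worsening comparisons, on top of the six responder comparisons already planned, all of them visibly late.
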